6.2. Exclusion Criteria

- 1) 5% or more blasts in the bone marrow or the presence of circulating blasts or current extramedullary involvement by AML.
- 2) History of relevant CNS pathology or current relevant CNS pathology (e.g. seizure, paresis, aphasia, cerebrovascular ischemia/haemorrhage, severe brain injuries, dementia, Parkinson's disease, cerebellar disease, organic brain syndrome, psychosis, coordination or movement disorder).
- 3) Current infiltration of cerebrospinal fluid by AML.
- 4) Body weight under 45kg
- 5) History of or active relevant autoimmune disease.
- 6) Prior allogeneic HSCT within the last 3 months prior to study treatment.
- 7) Systemic cancer chemotherapy within 2 weeks prior to study treatment.
- 8) Radiotherapy within 4 weeks prior to study treatment.
- 9) Treatment with any investigational product within four weeks prior to study treatment.
- 10) Previous treatment with blinatumomab.
- 11) Known hypersensitivity to immunoglobulins or to any other component of the study drug formulation.
- 12) History of malignancy other than AML within five years prior to treatment start with blinatumomab, with the exception of basal cell or squamous cell carcinoma of the skin, or carcinoma "in situ" of the cervix.

- 13) Active infection, any other concurrent disease or medical condition that are deemed to interfere with the conduct of the study as judged by the investigator.
- 14) Nursing women or those with a positive pregnancy test
- 15) Women of childbearing potential (as defined in CTFG guidelines, see appendix) not willing to use a highly effective form of contraception (as defined in CTFG guidelines) during participation in the study and for at least 3 months thereafter, or male patients not willing to ensure use of highly effective contraception during participation in the study and for at least three months thereafter.
- 16) Patients currently enrolled in another interventional clinical trial

6.3. Selection of Participants

Participants will be identified by their direct care team (most commonly their treating haematologist) at the hospital which they receive their care. If a participant is interested in taking part in the study, they will be referred to the trial investigators. In some circumstances the trial investigators may also be the direct care team for a patient.

6.4. Consent

The Chief Investigator or delegated clinician will inform the patient of all aspects pertaining to their participation in the study and that participation in the study is voluntary and that they can withdraw at any time. The patient's free and expressed informed consent will be obtained in writing prior to the screening procedures required for entry into the study according to all applicable regulatory requirements. The written Informed Consent Form must be dated and signed by both the investigator (or his designee) and the patient before any study related procedure will be initiated.

A copy of the signed consent form will be given to every subject, the original will be retained in the investigator site file and a copy will be filed in the patient's medical notes.

6.5. Screening logs

A screening log of all patients who were either ineligible or eligible but not consented will be so that any biases from differential recruitment will be detected.

Subject numbers will be allocated on Castor EDC.

6.6. Withdrawal of Participants

Participants have the right to withdraw consent for participation in any aspect of the trial at any time. The participants care will not be affected at any time by declining to participate or withdrawing from the trial. Withdrawn patients will be replaced to ensure that the study maintains sufficient statistical power.

The withdrawal of participant consent shall not affect the trial activities already carried out and the use of data/samples collected prior to participant withdrawal unless the patient requests that either the data or the samples or both are destroyed. Otherwise, the use of the data and samples collected prior to withdrawal of consent is based on informed consent before its withdrawal.

Furthermore, it is important to collect safety data ongoing at the time of withdrawal, especially if the participant withdraws because of a safety event. There is specific guidance on this contained in the Participant Information Sheet but briefly:

If a participant wishes to stop taking part in the trial completely, they will need attend a withdrawal visit. If the participant is suffering a serious reaction to the trial treatment when they decide to stop, you will need to continue to collect information about them for as long as the reaction lasts.

A participant may withdraw or be withdrawn from trial treatment for the following reasons:

- Intolerance to trial medication
- Withdrawal of consent for treatment by the participant
- Any alteration in the participants condition which justifies the discontinuation of the treatment in the Investigator's opinion
- Non-compliance

In all instances participants who consent and subsequently withdraw should complete a withdrawal form or this should be completed on the participant's behalf by the researcher/clinician based on information provided by the participant.

6.7. Expected Duration of Trial

The trial is expected to take 3 years to complete. The end of trial will be defined as the time of database lock.

6.8. Site and Investigator selection

This trial will be carried out at a single participating site during the first stage and up to two additional sites may be added by amendment for the second stage, depending on speed of enrolment

7. Trial Procedures

7.1. Screening

7.1.1. Eligibility Screening Period

Written informed consent must be obtained from each patient at or prior to the start of the 21-day screening period and before performance of any study-specific procedure. Standard of care MRD samples may be analysed prior to screening or enrolment onto this clinical trial.

All patients who have signed the Informed Consent Form (ICF) will be recorded on the Subject Screening Log. The patient is considered as being enrolled onto the study once written informed consent has been obtained. The eligibility screening period starts with the first study specific assessment after the ICF has been signed by the patient. Each patient will be assigned a unique patient identification number. If a patient is screened but not treated, the reason should be recorded. That patient's number will not be re-used.

Clinical assessments and laboratory assessment performed within 3 days prior to the first dose of blinatumomab will not have to be repeated on day 1 cycle 1. All results will be available before a patient will be declared eligible for study participation.

7.1.2. Eligibility Assessments

The following procedures and assessments must be performed during the screening period within three weeks prior to the first administration of the investigational product (Day 1):

Inclusion/Exclusion

Assessment of the patient's eligibility will be performed as outlined in section 6, including review of all laboratory measurements performed during the screening period. Eligibility will also need to be confirmed at treatment initiation.

Demographics

Date of birth, sex and ethnic origin will be recorded at screening.

Medical History/Current Medical Conditions

General and disease specific medical history including a history of past and current medical conditions, full history of the course of the patient's leukaemia including immunophenotype, karyotype, molecular phenotype, data on disease subset specifics, information on prior antitumour therapies and current eligibility for HSCT will be recorded at screening.

Physical Examination

Comprehensive physical examinations of all body systems will be performed at the screening visit.

Neurological Examination

During the screening visit a neurological examination will be performed including the test of the following functions: level of consciousness, orientation, vision, cranial nerves and brain stem functions, pyramidal and extrapyramidal motor system, reflexes, muscle tone and trophic findings, coordination, sensory system, neuropsychological findings (e.g., speech, cognition and emotion).

Writing Test

Patients will be asked to perform a writing test at screeningt in order to monitor patients for the onset and resolution of writing difficulties which may be an indicator for neurological AEs.

ECOG Performance Status

The patient's performance status will be assessed at screening using the Eastern Cooperative Oncology Group (ECOG) score.

Vital Signs

Body temperature, heart rate and blood pressure (systolic/diastolic) will be measured during screening

Electrocardiogram (ECG)

Standard 12-lead ECG will be performed at screening.

Blood tests

Blood samples for laboratory evaluations will be taken at screening. The following analyses will be performed:

- Serum chemistry
- Glucose, sodium, urea, uric acid, potassium, calcium, magnesium, phosphate, chloride, creatinine, total bilirubin, alkaline phosphatase (ALP), aspartate transaminase (AST), alanine transaminase (ALT), total serum protein, albumin, lactic dehydrogenase (LDH), C-reactive protein (CRP).
- Full blood count
- Coagulation screen
- Serum immunoglobulins (IgG)
- Creatinine clearance (e.g., determined by Cockroft and Gault) will be performed during the screening period to detect any severe kidney function impairment.

- Hepatitis B surface antigen (HBsAg), Hepatitis C virus (HCV) antibody and Human Immuno-deficiency Virus (HIV) testing will be performed during the screening period to exclude an untreated active infection with the respective viruses.

Urinalysis

The presence of glucose, protein and blood in urine will be assessed by dipstick during screening, at D1 prior to the start of infusion at each cycle, and at the End-of-Study visits.

Hepatitis B/C and HIV Testing

Pregnancy Test

A pregnancy test (β -human chorionic gonadotropin [β -HCG] in urine or serum) will be performed at screening in all women of childbearing potential. If at any time during the conduct of the study, a pregnancy is suspected, a pregnancy test should be performed immediately. Tests will be performed by the hospital's local laboratory. If results are positive the patient is ineligible and must be discontinued from study treatment immediately.

Bone marrow biopsy

A bone marrow aspirate, and trephine if necessary, will be performed during the screening period. Patients are potentially eligible for enrolment based on results of RT-qPCR assessment of the screening bone marrow aspirate and one of the following criteria must be fulfilled:

- Two consecutive positive samples with an increase in *RUNX1-RUNX1T1* transcript expression of more than 1 log₁₀ in a patient who previously tested negative in at least two technically adequate samples (molecular relapse)
- Two consecutive positive samples with an increase in *RUNX1-RUNX1T1* transcript expression of more than 1 log₁₀ in a patient who previously tested positive below a level of 500 copies / 10⁵ ABL (molecular progression)
- Two consecutive samples which both test positive at a level above 500 copies / 10⁵ ABL after the completion of primary therapy (molecular persistence of disease).

Concomitant Medication

All concomitant medications will be recorded starting at the first day of screening

7.2. Treatment Period (Cycle 1 - 4)

Patients will be hospitalised during at least the first three days of the first cycle and during at least the first two days of each following cycle. Before starting the infusion of blinatumomab, the patient will be examined physically and blood samples for safety laboratory parameters will be taken. For starting the study treatment the laboratory results will not have to be awaited.

Following the start of the infusion AE/SAE and concomitant medication will be evaluated continuously throughout the whole study until the 90-day visit. After the 90-day visit, only (S)AEs potentially related to blinatumomab should be documented in the CRF (and reported to the sponsor, if applicable). In addition, only anti-leukemic concomitant medication and medication related to blinatumomab related (serious) adverse events should be documented in the CRF. The vital signs and the laboratory tests will be repeated on D2 and D3 and at each visit during the treatment period.

Replacement of infusion bags will be performed as described in the Operations Manual. CADD pump infusion bags will be changed twice a week. To account for weekends and bank holidays, this will be on Tuesdays and Fridays. Each treatment cycle should begin on a Tuesday.

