5.5. Dosing Regimen

Patients will receive one to four consecutive cycles of blinatumomab. A cycle consists of a continuous intravenous infusion at a dose of 28 mcg/day over four weeks followed by an infusion free interval of two weeks. Patients will receive four cycles of treatment, unless criteria for treatment discontinuation apply. The duration of one cycle is 6 weeks, including a four week continuous intravenous infusion and a two week infusion free interval, which may be extended by a maximum of 7 days. In case of haematological relapse, the study treatment will be permanently discontinued. Patients are generally are expected to receive four cycles of treatment, independently from achieving complete molecular response. If patients are suitable for allogeneic HSCT after treatment with at least one treatment cycle of blinatumomab, they may undergo allogeneic HSCT instead of receiving further cycles with blinatumomab. Following the last treatment cycle, there will be a safety follow-up visit at 90 days after last infusion, documented as End-of-Core-Study Visit, followed by efficacy follow-up visits at three, six, nine, 12, 18 and 24 months after treatment start. Efficacy follow-up visits at six months will only be applicable for patients completing less than 4 cycles, at three months only for patients having completed 1 cycle only.

After completion of the two year efficacy follow-up period, information concerning haematological relapse free, leukaemia treatment free and overall survival as well as further data on hospitalisation and the use of relevant anti-leukemic, antibiotic, and antifungal medication and transfusion of blood products, and hospitalisation, if available, will be gathered by telephone at least every six months until death or at least until five years after treatment start, whichever occurs earlier. Patients who discontinue treatment prematurely

will enter immediately the efficacy and/or survival follow-up study. Patients who discontinue treatment before completion of the first treatment cycle will be assessed for MRD response on day 29 (and day 43, if applicable) of cycle 1 before entering the efficacy and/or survival follow-up study. In case of haematological relapse within the treatment period, treatment will be terminated at the time of relapse.

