5.13. Premedication

The clinical experience with blinatumomab has resulted in implementation of a premedication regimen described below:

Obligatory Pre-Medication:

- In adult patients, dexamethasone 20 mg intravenous should be administered 1 hour prior to initiation of each cycle of blinatumomab.
- Anti-pyretic use (e.g. paracetamol) is recommended to reduce pyrexia during the first 48 hours of each treatment cycle

During the treatment period:

In case of CNS-related events dexamethasone should be administered orally at a dose of at least 24 mg per day for up to three days. The dose will then be step-wise reduced over up to four days. If the CNS event was a seizure, appropriate prophylactic anticonvulsant treatment with a therapeutic dose of e.g. phenytoin or levetiracetam will be administered during restart and during start of the following new treatment cycle. For further information see Appendix.

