7.2.1. Treatment Period (Day 1 - Day 29 of each treatment cycle)

Prior to Infusion (D1)

- Physical examination
- Vital signs/temperature it is recommended to monitor the patient's vital signs continuously every four hours during the first 24 hours after start of treatment/dose step.
- Neurological examination and writing test
- Routine bloods, U/E, LFTs, LDH, Coagulations screen, FBC (aproximately 30mL of blood)
- Urinalysis
- Concomitant medication
- AE/SAE assessment
- CADD pump attachment

During Infusion (D2 to D22)

The following procedures and tests will be performed on D1 to D29 during blinatumomab infusion:

- Physical examination (D2, D3, D8, D15, D22)
- Vital signs/temperature (D2, D3, D8, D15, D22). On D2 and D3 vital signs should be measured at least twice a day
- Neurological examination and writing test (D2, D3, D8, D15, D22)
- Routine bloods, U/E, LFTs, LDH, Coagulations screen, FBC (D2, D3, D8, D15, D22) (aproximately 30mL of blood)
- Concomitant medication ()
- AE/SAE assessment ()
- CADD pump change on days 4, 8, 11, 15, 22 and 25

At the end of the infusion period of cycle two to four the procedures and tests of D29 of the first cycle will be repeated.

End of Infusion (D29)

The following procedures and tests will be performed on D29 (end of infusion):

- Physical examination
- Vital signs/temperature
- Neurological examination and writing test
- Bone marrow aspiration/biopsy
- Routine bloods, U/E, LFTs, LDH, Coagulations screen, FBC (aproximately 30mL of blood)
- Serum Immunoglobulins (IgG)
- Concomitant medication
- AE/SAE assessment

Infusion free Interval from Day 30 to Day 43 (applies to each treatment cycle)

After completion of the 4-week infusion period a 2-week infusion-free period will follow before a new cycle starts. During this time, the patient will not need to visit the study centre. The infusion free interval may be prolonged for up to seven more days, if deemed necessary. If the treatment will be continued, study day 43 of the previous cycle will be day 1 of the subsequent cycle.

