7.2.2. D43/D1 of Subsequent Cycle

If the treatment will be continued with a further cycle, the patient will be hospitalised for two days and the following procedures and tests will be performed:

- Physical examination
- ECOG performance status
- Neurological examination and writing test
- Vital signs/temperature
- Routine bloods, U/E, LFTs, LDH, Coagulations screen, FBC (aproximately 30mL of blood)
- Urinalysis
- Concomitant medication
- AE/SAE assessment
- Confirmatory bone marrow aspiration in case of central MRD result shows that the previous sample was technically inadequate.

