8.1. Definitions for Treatment Response Evaluation

- Complete molecular response is achieved if there is no amplification of *RUNX1-RUNX1T1* fusion transcripts in a technically adequate sample obtained after the first cycle of treatment.
- Two weeks after the first post treatment bone marrow sample was obtained (which is expected to be identical with day 1 of the second cycle), another bone marrow aspiration has to be obtained in case the previous specimen was technically suboptimal and did not allow evaluation for molecular complete response.
- Molecular relapse is defined as re-appearance of *RUNX1-RUNX1T1* fusion transcripts on two consecutive samples with an increase in transcript expression of

- more than 1 log₁₀ in a patient who previously tested negative in at least two technically adequate samples
- Molecular progression is defined as an increase in disease-related transcript expression levels of more than 1 log₁₀ confirmed on a second consecutive sample.
- Haematological relapse is defined as unequivocal detection of > 5% leukaemia cells in bone marrow as measured by cytological, microscopic assessment, presence of circulating leukaemia blasts, or extramedullary leukaemia.

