8.3. Bone Marrow Aspiration

Evaluation of MRD will be performed on bone marrow aspirate samples. Each bone marrow will be evaluated for presence of leukaemia cells with differential count by light microscopy at the local laboratory and results entered on the CRF.

At the end of the first treatment cycle (D29) a bone marrow aspiration will be performed and shipped to the central MRD laboratory for the evaluation of the primary endpoint. In case of technically suboptimal samples (i.e. *ABL* Ct >26), a second bone marrow aspiration will be performed to confirm whether the primary endpoint of complete molecular response was reached or not.

At the end of each treatment cycle (D29) and during the efficacy follow-up visits a bone marrow aspiration will be performed to evaluate MRD and morphology defining the percentage of leukemic blasts in bone marrow. Furthermore, in the event of abnormal blood counts (suggesting leukemic relapse), a bone marrow evaluation should be performed prior to initiating the subsequent cycle of treatment with blinatumomab.

Additional tests conducted by the investigators but not required by protocol such as immunophenotypic, cytogenetic or molecular analyses during the study will be collected and documented in the CRF. During the study, haematological/morphological assessments of the bone marrow will be performed locally.

9. Assessment of Safety

Adverse events (AEs) will be reported from the time of consent up to ninety days after the completion of the final dose of Blinatumomab.

All serious adverse events (SAEs) must be reported immediately (and within 24 hours of knowledge of the event) by the PI at the participating site to the Clinical Trials Office (CTO).

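### Section 7.2 lets cycles 2 to 4 start before the day 43/day 1 blood count is read, although section 8.3 wants a marrow first if counts suggest relapse

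*Protocol*

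**What the plan says.** **Starting an infusion.** Protocol section 7.2 is headed for cycles 1 to 4, and its opening paragraph deals with the first cycle and those that follow. The patient is examined and safety bloods are drawn before the infusion, but "For starting the study treatment the laboratory results will not have to be awaited".

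**Suspected relapse between cycles.** Section 8.3 schedules a marrow on day 29 of every cycle. It then adds that "in the event of abnormal blood counts (suggesting leukemic relapse), a bone marrow evaluation should be performed prior to initiating the subsequent cycle".

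**The break.** For days 30 to 42, section 7.2.1 says: "During this time, the patient will not need to visit the study centre". The schedule of events (4.5) shows no haematology or biochemistry in that column. Day 43 of one cycle is day 1 of the next.

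**Day 43/day 1.** Section 7.2.2 lists a full blood count. The only marrow it lists is: "Confirmatory bone marrow aspiration in case of central MRD result shows that the previous sample was technically inadequate".

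**Consequence of relapse.** Under section 8.1, "presence of circulating leukaemia blasts, or extramedullary leukaemia" each suffice for haematological relapse, as an alternative to marrow blasts above 5%. Section 5.5 then states: "In case of haematological relapse, the study treatment will be permanently discontinued".

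**The concern.** The section 8.3 instruction depends on someone knowing the blood count before the next cycle starts. Section 7.2 permits the cycle to start without that knowledge. A site that follows 7.2 as written can connect the pump and learn later that day, or the next, that a marrow was due first. If the count shows circulating leukaemia blasts, the patient already meets the relapse definition and should not have started the cycle.

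What is at stake is patient safety and consistent conduct. The primary endpoint is read from the day 29 marrow of cycle 1, before any of these starts, so neither it nor the two-stage decision rule is touched.

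**Working it through.** The protocol gives no figure to reproduce here. The check is a reading of the sections against each other and a count of days.

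**1. Which scheduled counts could trigger the 8.3 marrow?** Every patient has a marrow with morphology on day 29, whatever the counts show. The count-triggered marrow therefore adds something mainly when counts change after day 29. Sections 4.5 and 7.2.1 schedule no bloods on days 30 to 42, and the 90-day and efficacy follow-up visits come after the last cycle. That leaves the day 43/day 1 count, apart from any unscheduled test.

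**2. Must that count be read before the infusion?** Section 7.2 says results need not be awaited. Section 7.2.2 lists the count without a review step. No other section supplies one for cycles 2 to 4.

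**3. Is cycle 1 different?** Yes. Section 7.1.1 requires all results before a patient is declared eligible, and section 7.1.2 has eligibility confirmed at treatment initiation. Assessments "performed within 3 days prior to the first dose of blinatumomab will not have to be repeated on day 1 cycle 1". The permission in 7.2 is reasonable for cycle 1. These safeguards concern trial entry and do not carry over to later cycles.

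**4. How old is the newest scheduled count when the next cycle starts?** Inputs: day 29 with a window of ±2 days (4.5); next cycle on day 43 (7.2.1); break extendable by up to 7 days, so a start as late as day 50 (5.5, 7.2.1). Age = start day − day of last count.

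| Start of next cycle | Nominal (day 29) | Late visit (day 31) | Early visit (day 27) |
|---|---|---|---|
| Day 43 | 43 − 29 = 14 days | 43 − 31 = 12 days | 43 − 27 = 16 days |
| Day 50 (7-day extension) | 50 − 29 = 21 days | 50 − 31 = 19 days | 50 − 27 = 23 days |

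These ages treat the start day as fixed when the day 29 visit moves within its window.

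**5. When would a missed result surface?** The day 1 result itself should come back during the admission. The next scheduled count is day 2, one day later.

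**6. How often would this happen?** The protocol gives no rate at which counts become abnormal during the break, so no number or ceiling of affected starts can be given.

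**The case against.** **The 7.2 sentence may concern the first dose only.** Exclusion criteria 6 to 9 use the term study treatment for the first dose, section 5.5 counts follow-up from the one treatment start, and sections 5.6 and 8.3 use other words for later cycles. This reading is possible. It is the weaker one, because the heading and the opening sentence of the same paragraph take in all four cycles. If it were right, cycles 2 to 4 would simply have no rule on reading the count.

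**There is no strict contradiction.** Section 7.2 permits and does not oblige; a careful site can wait for the count and satisfy both sections. That stands. The defect is that 7.2 expressly permits skipping the information on which 8.3 depends.

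**Other controls cover most of the risk.** These are the day 29 marrow and count, the examination before infusion, at least two inpatient days, repeat bloods on days 2 and 3, unscheduled visits for symptoms, and the stopping rules in 5.9. This also stands, and it is why the point is minor. No harm from a few hours of infusion is shown.

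**The remedy is partial.** It has a marrow performed before the infusion but does not require the morphology to be read. That is true, but section 8.3 itself asks only that the marrow be performed. The change makes the protocol deliver what it already intends.

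**Conclusion.** The concern holds as a minor one. On the more natural reading, section 7.2 allows cycles 2 to 4 to start before anyone has seen the only scheduled count that could call for the section 8.3 marrow. The last scheduled count already known is then 12 to 16 days old, or 19 to 23 days with a full extension of the break.

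The effect needs a change that first appears after day 29 and is not picked up at an unscheduled visit. The likely consequence is some hours of infusion before the result is acted on; that duration is a judgement from the inpatient start and the day 2 bloods, not a figure in the protocol. Neither the primary endpoint nor the Simon design is affected. The conclusion assumes that the 7.2 sentence applies to all cycles, as its heading suggests.

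**What to change.** Make two wording changes.

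- **Section 7.2**, after the sentence on not awaiting results: *For cycles 2 to 4, the full blood count from D43/D1, or from within 3 days before it, must be reviewed before the infusion starts. Other day 1 results need not be awaited.*
- **Section 7.2.2**, at the end of the marrow bullet: *or if blood counts suggest relapse (see 8.3), before the infusion starts.*

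No new test is needed: the count is already drawn and the patient is already admitted that day. The cost is a possible delay of some hours on day 1. Part of that time is already in the schedule, since section 5.13 says "dexamethasone 20 mg intravenous should be administered 1 hour prior to initiation of each cycle of blinatumomab". Using a sample from the 3 days before avoids the delay. Because cycles start on a Tuesday, those days are Saturday, Sunday and Monday, so in practice it means one extra Monday visit in a break that the protocol otherwise keeps free of visits.
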